7.3 Assessment and Verification of Compliance

Site staff will administer all IPs IV at the study center. The dose and date of administration of IP must be recorded in the subject eCRF. Treatment compliance will be assessed based on this information.

7.4 Prohibited and Restricted Therapies

Medications that are considered necessary for the safety and well-being of subjects may be given at the discretion of the Investigator, and recorded in the appropriate section of the eCRF. Use of treatments listed below may lead to IP discontinuation. Subjects should not start taking any of the following without discussing with the Investigator:

- 1. Naturopathic, herbal, or ayurvedic remedies.
- 2. Nutritional or dietary supplements
- 3. Vitamins and/or minerals.

7.4.1 Medications Leading to Immediate Discontinuation of Investigational Product for Both Populations

Receipt of any of these medications leads to immediate discontinuation of IP:

- Investigational agents
- Immunosuppressants with the exceptions listed below
- Biologic immunomodulators (including belimumab, abatacept, rituximab)
- Live or attenuated vaccines (the Sponsor recommends that Investigators ensure all subjects are up-to-date with required vaccinations prior to entry into the study)
- Plasmapheresis/Plasma exchange
- Any Ig therapy
- Corticosteroids > 0.5 mg/kg/day or > 40 mg/day prednisone-equivalent

7.4.2 Restricted Medications in Population #1

If a subject receives any of the following after randomization, the Investigator must notify the Sponsor/Designee Medical Monitor immediately. The Medical Monitor will determine with the Sponsor if the subject may continue to receive IP, however, the subject would be considered a non-responder for binary assessments.

- AZA > 150 mg/day, MTX > 20 mg/week, leflunomide > 40 mg/day, MMF > 2gm/day, hydroxychloroquine > 400 mg/day OR any increase from baseline (including initiation of treatment)
- Prednisone > 10 mg/day OR any increase from baseline (including initiation of treatment)

- Initiation of any new cDMARD
- Corticosteroids with a long biologic half-life (eg, dexamethasone, betamethasone)

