7.4.3 Rescue Medications for Population #1

The initiation or increase in dose of the restricted medications in Section 7.4.2 are also considered as rescue medications for Population #1.

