3.4.4 Prior and Concomitant Medications

Number (%) of subjects who receive prior medications and concomitant medications during Stage I and during Stage II + Off-treatment follow-up period will be summarized by world health organization (WHO) Drug dictionary Anatomical Therapeutic Chemical (ATC) category and PT. At each level of summarization, a subject is counted once if he/she reported one or more medications at that level. The summary of prior medications and concomitant medications during Stage I will be based on the safety analysis set. The summary of concomitant medications during Stage II + Off-treatment follow-up period will be based on the cross-over analysis set.

The prior and concomitant medications are defined as below.

- Prior medications are defined as medications with a stop date occurring before the first IP administration date.
- Concomitant medications during Stage I are defined as follows:
 - Medications with a start date before the Day 169 IP administration date and stop date on or after the first IP administration date for subjects entering Stage II.
 - Medications with a stop date on or after the first IP administration date for subjects not entering Stage II.

• Concomitant medications during Stage II + Off-treatment follow-up period are defined as medications with a stop date on or after the Day 169 IP administration date.

Use of disease-related medications at baseline, defined as all disease-related medications with an intake at the date of first dose of IP (ie, start date on or before the date of first dose and end date on or after date of first dose or ongoing) will be summarized for the full analysis set. The number and percentage of subjects who receive rescue medication during Stage I and during Stage II + Off-treatment follow-up period will also be summarized for the full analysis set and cross-over analysis set respectively.

Rescue medications for population #1 are listed below:

- Azathioprine (AZA) > 150 mg/day, methotrexate (MTX) > 20 mg/week, leflunomide >20 mg/day, mycophenolate mofetil (MMF) > 2gm/day OR any increase from baseline (including initiation of treatment)
- Any increase from baseline in anti-malarial (including initiation of treatment)
- Initiation of any new conventional disease-modifying anti-rheumatic drug (cDMARD)
- Oral prednisone > 10 mg/day OR any increase from baseline (including initiation of treatment)
- Intramuscular, IV, or intraarticular corticosteroids

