- Corticosteroids with a long biologic half-life (eg, dexamethasone, betamethasone)

Rescue medications for population #2 are listed below:

- Oral, intramuscular, IV, or intraarticular corticosteroids
- MTX, AZA, leflunomide, MMF, and other cDMARD or immunosuppressive or antiproliferative medications
- Any increase from baseline in anti-malarial (including initiation of treatment)
- Any increase or initiation of new doses of cevimeline or pilocarpine and cyclosporine eye drops (Restasis)

The missing start/stop date of medications will be imputed as appropriate and the details of the imputation will be included in the SPP.

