3.5.1.3 Handling plan for Intercurrent Events

Rescue medication use:

For subjects who take rescue medications defined in section 3.4.4 before Day 169, the data collected after administration of the rescue medications will not be included in the primary analysis. This approach attempts to reduce the confounding effects of rescue medications.

Treatment discontinuation:

Subjects who discontinue IP before Day 169 will be asked to come to scheduled evaluations until Day 169 visit and at least 3 months of off-treatment follow-up after the last IP administration. The data collected after discontinuation of study treatment will be included in the analysis.

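### The Population #1 oral-steroid rescue line names prednisone without equivalents, so read literally, starting or raising prednisolone or methylprednisolone is not rescue

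*Protocol*

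**What the plan says.** The rescue definition for Population #1 stands in two places.

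- Protocol 7.4.2 restricts "Prednisone > 10 mg/day OR any increase from baseline (including initiation of treatment". Section 7.4.3 turns that list into rescue: "The initiation or increase in dose of the restricted medications in Section 7.4.2 are also considered as rescue medications for Population #1".
- SAP 3.4.4 has the line "Oral prednisone > 10 mg/day OR any increase from baseline (including initiation of treatment". Two further lines there cover "Intramuscular, IV, or intraarticular corticosteroids" and "Corticosteroids with a long biologic half-life (eg, dexamethasone, betamethasone".

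SAP 3.5.1.3 makes the SAP list the operative one. The rule applies "For subjects who take rescue medications defined in section 3.4.4 before Day 169", and for them "the data collected after administration of the rescue medications will not be included in the primary analysis". The stated aim is to limit confounding by rescue. For subjects who stop investigational product (IP), the opposite rule holds: "The data collected after discontinuation of study treatment will be included in the analysis".

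Elsewhere the protocol counts steroids in prednisone equivalents. Exclusion item 15 in section 5.1.2 does so for the background dose of up to 10 mg/day, and section 7.4.1 does so for the dose that stops IP. The Population #2 list covers oral corticosteroids of any kind.

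**The concern.** Item 15 lets a subject enter Population #1 on background prednisolone, but an increase in that drug matches no line of the rescue list. The same holds for starting any oral corticosteroid that is neither prednisone nor long-acting. One steroid course is therefore rescue or not rescue according to the name of the drug.

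Three rules depend on the list:

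- the exclusion of post-rescue data from the primary mixed model (SAP 3.5.1.3);
- the worst-score imputation in the sensitivity analysis (SAP 3.5.1.5);
- the ESSDAI[3] and ESSDAI[4] response, which requires no rescue (SAP 3.5.2.1).

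Read literally, the first keeps these subjects' later values, the second imputes nothing for them, and the third can still count them as responders. The include-all sensitivity analysis and the time-adjusted AUC analysis do not use the list and are unaffected.

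**Working it through.** **Text check.** Each kind of steroid use in Population #1, set against SAP 3.4.4:

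| Use after randomization | Matching line |
|---|---|
| Prednisone started, increased, or above 10 mg/day | Oral prednisone line |
| Intramuscular, IV or intraarticular corticosteroid | Injected line |
| Oral dexamethasone or betamethasone | Long half-life line |
| Oral prednisolone or methylprednisolone, started or increased | None |

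The stop rule in 7.4.1 does not close the gap. A subject on more than 40 mg/day prednisone-equivalent of oral prednisolone must stop IP, but data after IP discontinuation are kept.

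**The plan's own figure.** Protocol 10.3 gives a difference of 3.0, SD 5, two-sided alpha 0.10, 36 per arm and a two-sample t-test. The standard error is 5 × √(2/36) = 1.179, the noncentrality is 3.0/1.179 = 2.546, and the critical value on 70 df is 1.667. The noncentral t gives 81.0% power (stated: 80%). The minimum detectable difference is 1.667 × 1.179 = 1.96 (stated: 2.0). Both reproduce.

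**Illustrations.** The documents give no rate of unlisted oral steroid use, no split by arm and no steroid effect on ESSDAI, so the inputs below are assumptions. Let b be the points by which the steroid lowers a subject's Day 169 ESSDAI.

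- Kept: difference = 3.0 − (placebo cases − VIB4920 cases) × b/36, with 36 per arm.
- Excluded: difference = 3.0 with the cases removed from each arm, if missing at random holds.

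| Cases, placebo v VIB4920 | b | Difference if kept | Power if kept | Power if excluded (n placebo v VIB4920) |
|---|---|---|---|---|
| 1 v 0 | 3 | 3.0 − 3/36 = 2.917 | 79.0% | 80.5% (35 v 36) |
| 2 v 1 | 3 | 3.0 − 3/36 = 2.917 | 79.0% | 79.4% (34 v 35) |
| 2 v 1 | 5 | 3.0 − 5/36 = 2.861 | 77.6% | 79.4% (34 v 35) |
| 1 v 1 | any | 3.0 | 81.0% | 80.0% (35 v 35) |
| 2 v 2 | any | 3.0 | 81.0% | 78.9% (34 v 34) |
| 4 v 4 | any | 3.0 | 81.0% | 76.7% (32 v 32) |
| 0 v 1 | 3 | 3.0 + 3/36 = 3.083 | 82.8% | 80.5% (36 v 35) |

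Protocol 10.5.1 relies on missing at random. If that assumption is wrong by 3 points for the one excluded placebo case, the excluded analysis gives 3.0 − 3/36 = 2.917 with 35 v 36, and power is 78.5%. That is no better than the 79.0% from keeping the value.

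The SD is held at 5 throughout. The mixed model may recover part of the excluded information from earlier visits.

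**The case against.** The strongest reply is that this is only a wording matter. The rescue line shares its 10 mg/day limit with item 15, and an increase from baseline most naturally refers to the background dose that item 15 counts in equivalents. Programmers may well map equivalents anyway. The affected group is narrow, every scenario input is assumed, and the illustrations show no consistent gain from exclusion. Two planned analyses do not depend on the list at all. Placing prednisolone and methylprednisolone outside the long half-life line also rests on general pharmacology, since the documents give only dexamethasone and betamethasone as examples.

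Most of this stands as a limit on size. It does not remove the gap. If equivalents are intended, the list should say so. Otherwise someone must decide case by case whether a course was rescue, and by what conversion, with an interim unblinding planned.

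Two practical points also stand. Amending Protocol 7.4.2 is not needed for the primary analysis, because SAP 3.4.4 governs it and already departs from 7.4.2 (leflunomide above 20 rather than 40 mg/day, and injected steroids added). And the documents do not show whether the interim database lock has passed.

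**Conclusion.** The concern holds. Read literally, the Population #1 rescue list does not cover starting or increasing an oral corticosteroid that is neither prednisone nor long-acting. The primary analysis, the worst-score analysis and the ESSDAI response endpoints inherit that gap. Population #2 has none.

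The effect is unknown and probably small. Its direction depends on which arm uses more of these drugs: more use on placebo dilutes the difference, more on VIB4920 inflates it, and equal use leaves it unchanged if the steroid effect is the same in both arms. Exclusion restores the difference only if missing at random holds. The case for changing the line is consistency with the plan's own exclusion rule. It should be changed, but it calls for no redesign.

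**What to change.** In SAP 3.4.4, replace the Population #1 oral line with: *oral corticosteroids > 10 mg/day prednisone or equivalent, or any increase from baseline in total daily prednisone-equivalent dose, including initiation*. Counting the total equivalent dose means that a switch between drugs at the same dose is not rescue. Fix one conversion table in the statistical programming plan before the interim database lock. If that lock has passed, staff without access to unblinded results should make the change, and it should be dated.

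Concomitant medications are recorded at every visit (Protocol Table 2), so no new data are needed. Align Protocol 7.4.2 at the next amendment; that step also extends Medical Monitor notification, the decision on continuing IP, and non-responder status to these drugs.

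The statistical cost is the loss of a few more subjects' post-rescue data. Under the same assumptions, against 81.0%:

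- 2 to 4 placebo subjects only: about 1 to 2 points of power (2 v 0 costs 1.0, 4 v 0 costs 2.2);
- half as many on VIB4920: about 1.5 to 3 points (2 v 1 costs 1.5, 4 v 2 costs 3.2);
- 2 to 4 in each arm: about 2 to 4 points (2 v 2 costs 2.0, 4 v 4 costs 4.3).

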7.4.3 Rescue Medications for Population #1

The initiation or increase in dose of the restricted medications in Section 7.4.2 are also considered as rescue medications for Population #1.

7.4.4 Restricted Medications in Population #2

If a subject receives any of the following after randomization, the Investigator must notify the Sponsor/Designee Medical Monitor immediately. The Medical Monitor will determine with the Sponsor if the subject may continue to receive IP, however, the subject would be considered a non-responder for binary assessments.

- Oral, intramuscular, IV, or intra-articular corticosteroids
- MTX, AZA, leflunomide MMF, and other cDMARD or immunosuppressive or antiproliferative medications.
- Any medication that in the opinion of the Investigator would interfere with evaluation of the IP or interpretation of subject safety or study results
- Any increase or initiation of new doses of cevimeline or pilocarpine and cyclosporine eye drops (Restasis).

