 - d. Any medication that in the opinion of the Investigator would interfere with evaluation of the IP or interpretation of subject safety or study results
 - e. Any increase or initiation of a new dose of regularly scheduled nonsteroidal antiinflammatory drugs within 2 weeks prior to signing the ICF through randomization (Day 1).
 - f. Any increase or initiation of new doses of cevimeline or pilocarpine and cyclosporine eye drops (Restasis) within 2 weeks prior to signing the ICF through randomization (Day 1).
- 16. Subjects who have received previous treatment with anti-CD40L compounds at any time before screening.
- 17. Subjects with blood tests, at screening, of any of the following:
 - AST $> 2 \times ULN$
 - $ALT > 2 \times ULN$
 - TBL $> 2 \times ULN$
 - Hemoglobin < 75 g/L
 - Neutrophils $< 1.0 \times 109/L$
 - Platelets < 100 x 109/L
 - Prothrombin or PTT > ULN

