7.4.5 Rescue Medications for Population #2

The initiation or increase in dose of the restricted medications in Section 7.4.4 are also considered as rescue medications for Population #2.

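### The SAP rescue list does not carry out the protocol's non-responder rule for investigator-judged interfering medication in Population #2, nor for stable hydroxychloroquine above 400 mg/day in Population #1

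*Protocol*

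**What the plan says.** **Protocol.** Sections 7.4.2 (Population #1) and 7.4.4 (Population #2) list restricted medications. If a subject receives one after randomization, the site must notify the Medical Monitor at once. Dosing may or may not continue, but in either case "the subject would be considered a non-responder for binary assessments". The Population #2 list includes "Any medication that in the opinion of the Investigator would interfere with evaluation of the IP"; the same item also covers drugs that would interfere with interpreting safety or study results. Section 7.4.5 then links restriction to rescue: "The initiation or increase in dose of the restricted medications in Section 7.4.4 are also considered as rescue medications for Population #2". Section 7.4.3 does the same for Population #1. Section 10.5.1 removes data collected after rescue from the primary analysis.

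**SAP.** Section 3.4.4 does not refer back to those protocol lists. It states that "Rescue medications for population #2 are listed below" and gives four items: oral or injected corticosteroids; methotrexate and other immunosuppressive drugs; an antimalarial start or increase; and a start or increase of cevimeline, pilocarpine or cyclosporine eye drops. The investigator-opinion item is not among them. Section 3.5.1.3 cites 3.4.4 by number for the primary-analysis exclusion. Section 3.5.2.1 requires responders to have received no rescue medication. It cites no section, but 3.4.4 holds the only rescue lists in the SAP.

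**The concern.** The protocol attaches a definite consequence to a restricted medication: the subject is a non-responder. If the SAP list is shorter than the protocol list, programming from the SAP does not apply that consequence, and nothing in the SAP says that this was intended.

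Three secondary endpoints depend on it: ESSDAI[3] and ESSDAI[4] response in Population #1 and ESSPRI response in Population #2. No modelled analysis of these is free of the rescue list. If the discrepancy is noticed only after unblinding, deciding which document governs becomes a post hoc choice.

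A hypothetical case shows why the omitted item could matter. At entry, Population #2 excludes "Any increase or initiation of a new dose of regularly scheduled nonsteroidal antiinflammatory drugs" within two weeks before consent through randomization. Neither rescue list names these drugs, so the investigator-opinion item is the only listed route by which a new one could count. Pain is one of three equally weighted ESSPRI items.

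**Working it through.** **Step 1. Compare the lists.** They differ in five places.

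| Item | Protocol 7.4.2 to 7.4.5 | SAP 3.4.4 | Does status differ? |
|---|---|---|---|
| Population #2: drug the Investigator judges to interfere | Non-response on receipt; start or increase is rescue | Not listed | Yes. Can be an ESSPRI responder under the SAP, and later ESSPRI values stay in the primary model |
| Population #1: antimalarials | Hydroxychloroquine > 400 mg/day, or any increase | Any antimalarial increase, no dose limit | Yes for a stable dose > 400 mg/day, but for responder status only |
| Population #1: injected corticosteroids | Not named, apart from prednisone and long half-life agents | Listed: "Intramuscular, IV, or intraarticular corticosteroids" | SAP addition; the SAP rule governs |
| Population #1: leflunomide limit | > 40 mg/day | > 20 mg/day | No |
| Population #2: antimalarials | Not named; may fall under other cDMARDs | Any start or increase | Depends on the reading |

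**Step 2. Test the Population #1 rows against the entry criteria (Protocol 5.1.2).**

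- Leflunomide: exclusion 17d bars entry above 20 mg/day, and both lists count any increase. Every dose above 20 mg/day after entry is therefore an increase and is caught by both.
- Hydroxychloroquine: exclusion 17a requires a stable dose but sets no upper limit, so a subject can enter above 400 mg/day. On the literal text of 7.4.2 that subject is a non-responder. Protocol 7.4.3 needs a start or increase, so the stable dose is rescue under neither document. Only the non-responder sentence separates them.

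**Step 3. Trace which analyses use the list.** Each primary endpoint has four planned analyses.

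- Two depend on the list: the primary model and the worst-score imputation.
- Two do not: the analysis that includes all data after rescue, and the time-adjusted AUC (SAP 3.5.1.5).
- The responder analyses (SAP 3.5.2.2) all depend on it. The ESSDAI and ESSPRI cumulative distribution plots (SAP 3.5.5) state no rescue exclusion, but they are descriptive.

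**Step 4. Size per subject.** The inputs are the planned arm sizes in Protocol 10.3 and SAP 2.3: 36 and 51 per arm. The stated 80% power reproduces at these sizes with a two-sample t-test (0.810 and 0.806). Let r be the number of subjects in an arm who took a drug on which the documents disagree, met the score threshold and stayed in the study.

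- Shift in that arm's responder rate = r/n
- Population #1, r = 1: 1/36 = 0.028, or 2.8 percentage points
- Population #2, r = 1: 1/51 = 0.020, or 2.0 percentage points
- Shift in the treatment difference = (r in the VIB4920 arm − r in the placebo arm)/n, which is zero when the two counts are equal

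**Step 5. The pain example.** ESSPRI is the mean of three items. A 3-point fall in pain alone gives 3/3 = 1.0 point, which meets the ≥ 1 point response threshold with no change in dryness or fatigue. This shows that the case is possible, not how often it would occur.

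**The case against.** **The SAP may add detail.** Protocol 10.1 leaves further statistical detail to the SAP, and 7.4.3 does not call its list complete. This stands for injected corticosteroids in Population #1. A reader might infer that the two documents contradict each other there, but the SAP adds an item and its list is the one programmed. It does not stand for the investigator-opinion item: adding detail is different from leaving out a stated non-responder rule.

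**A fixed list is better for the primary analysis.** The opinion item is open-ended, is judged after randomization, and covers safety interpretation as well as efficacy. Using it to delete ESSPRI values could discard valid data after drugs with no bearing on symptoms. This stands, and it narrows the remedy: the protocol's explicit consequence concerns binary assessments only.

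**The primary result is already protected.** Two of the four analyses of each primary endpoint ignore the list. Concomitant medications are tabulated (SAP 3.4.4), and prohibited medication is among the listed major deviations (SAP 3.2). This stands for the primary endpoints. It does not give the responder endpoints a list-free model.

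**The anti-inflammatory example is hypothetical.** Agreed. Nothing shows that Investigators would judge such a drug to interfere.

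**Conclusion.** There is one clear conflict. In Population #2, receipt of an investigator-judged interfering drug is non-response under Protocol 7.4.4, yet that subject can be an ESSPRI responder under the SAP. A narrower one is stable hydroxychloroquine above 400 mg/day in Population #1. The rest needs alignment only: the leflunomide limit has no effect, and the antimalarial wording otherwise has little.

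The numerical effect is unknown, because the documents give no frequency for any of these drugs. All that can be said is 2.0 points (Population #2) or 2.8 points (Population #1) in an arm per affected would-be responder, assuming that all randomized subjects are dosed and so enter the full analysis set.

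The documents do not support three stronger readings that a reader might infer:

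- That all five list differences change a subject's status. Step 2 removes leflunomide. The Population #2 antimalarial item turns on whether these drugs count as other cDMARDs. Exclusions 15a and 15c list the two separately, but the protocol does not settle it.
- That the primary analysis has no defined rule. SAP 3.5.1.3 names one list. What is missing is a statement that it departs from Protocol 7.4.5.
- That the treatment effect is biased by some number of points. This would need assumed counts and an assumed imbalance between arms. If the affected subjects are spread evenly, the difference may barely move.

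This is a consistency correction, worth making because it is cheap and is best settled under blind.

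**What to change.** Make the SAP change before the Day 85 interim unblinding. If that has passed, blinded personnel should make it before the primary analysis.

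1. **Responder definitions (SAP 3.5.2.1).** Keep the existing conditions and add that receipt of any medication restricted by Protocol 7.4.2 or 7.4.4 by Day 169 is non-response. This covers stable hydroxychloroquine above 400 mg/day and the Population #2 investigator-opinion item. Identify the latter under blind from the Medical Monitor notifications that 7.4.4 already requires.
2. **Primary-analysis exclusion (SAP 3.5.1.3).** Keep the fixed 3.4.4 list and record the omission of the opinion item as a departure from Protocol 7.4.5. Alternatively, add the item only for drugs judged under blind to affect ESSPRI. The choice is for the sponsor's clinical team.
3. **Protocol wording.** At the next amendment, align the injected-corticosteroid, leflunomide and antimalarial wording in 7.4.2 and 7.4.4.

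Items 1 and 2 cost a small SAP revision and a blinded medication review, with no new visits or samples. Item 3 needs ethics re-approval (Protocol 11.2) across approximately 70 sites and adds drugs to the notification duty, so it can wait.
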